PROTOCOL TITLE: Visual Outcomes and Patient Satisfaction with Vivity IOL in Post Refractive Patients

PROTOCOL # 69865263

STUDY TREATMENTS: Non-interventional (None).

Background:

The Vivity IOL provides excellent distance and intermediate vision, but some surgeons are hesitant to implant the IOL in post-refractive patients, the majority of which are post-operative myopic LASIK/PRK. Those surgeons may have the concern that the elevated spherical aberration or other high order aberrations may lead to decreased visual outcomes or increased visual disturbances.

Clinical Hypothesis:

The hypothesis is that post-myopic refractive patients that have high spherical aberration (SAs) will have excellent outcomes and satisfaction with a Vivity IOL.

Scientific Rationale:

Patients typically have increased higher order aberrations (HOAs), in particular, higher spherical aberration after myopic refractive surgery (LASIK/PRK).

Study Objectives:

The objective of this study is to test the hypothesis that the Vivity non-diffractive Extended Vision IOL performs well in patients that had prior myopic refractive surgery and high residual SA after the refractive procedure.

OVERALL STUDY DESIGN

This is a non-interventional, prospective, single center, bilateral, observational study of the outcomes for 40 post myopic refractive surgery patients following successful, uncomplicated cataract surgery with bilateral implantation of the Vivity IOL (DAT***/CCWET*) performed by 4 surgeons using similar surgical techniques. 40 subjects will be enrolled.

Duration:

12 months or longer to meet required enrollment.

Administration:

Patients with healthy eyes and a history of myopic LASIK or PRK with a spherical aberration greater than 0.3 as measured by the Atlas topographer who meet the inclusion criteria and have had bilateral Vivity IOLs implanted at the time of cataract surgery will be offered the opportunity to participate in the study.

Visit Schedule:

All subjects will undergo 1 visit. At the study visit and after informed consent, the subjects' demographic information will be collected, and the subject will have the following testing:

- 1) Manifest refraction
- 2) Distance corrected binocular distance (best corrected), intermediate (60 cm), and near (40 cm) visual acuity
- 3) Monocular and binocular distance corrected (best corrected) monocular distance visual acuity
- 4) Uncorrected monocular and binocular distance, intermediate (60 cm), and near (40 cm) visual acuity
- 5) Binocular defocus curve (+1.00 D to -3.00 D, 0.5 D steps)
- 6) Binocular best corrected distance visual acuity in mesopic lighting
- 7) Patient survey regarding satisfaction and glare, halos, starbursts using IOLSAT and QUVID questionnaires, respectively
- 8) Self-reported visual disturbance questionnaire
- 9) Atlas topography; potentially additional topography/tomography with iTrace and/or pentacam

STUDY POPULATION CHARACTERISTICS:

Condition

Patients with healthy eyes, prior myopic LASIK or PRK with SA greater than 0.3, and uncomplicated bilateral implantation of the Vivity IOL (DAT***/CCWET*).

Number of Subjects:

This is a non-interventional, observational study with 40 patients (80 eyes).

Inclusion/Exclusion Criteria (all study criteria apply to each study eye unless otherwise indicated):

Inclusions

- 1) Adults, 40 years of age having already undergone cataract removal by phacoemulsification with a clear corneal incision in both eyes with implantation of the Vivity IOL (DAT***/CCWET*)
- 2) Prior uncomplicated, distance-targeted, bilateral myopic LASIK or PRK surgery and corneal spherical aberration greater than $\geq 0.30 \mu$ and $\leq 1.20 \mu$ in at least one eye (6.00 mm) as measured at their cataract pre-op visit
- 3) Able to comprehend and willing to sign informed consent and complete all required testing procedures
- 4) Best Corrected Distance Visual Acuity (BCDVA) projected to be 0.10 logMAR (Minimum Angle of Resolution) or better

- 5) Clear intraocular media
- 6) Minimum of two weeks post YAG capsulotomy to treat PCO
- 7) Residual refractive astigmatism ≤ 0.50 diopters
- 8) Post-operative refractive spherical equivalent from +0.50 to -0.50 SE

Exclusions

Subjects will not be permitted to enroll in this study if they meet any of the following exclusion criteria:

- 1) Any corneal abnormality, other than regular corneal astigmatism or myopic LASIK/PRK surgery, (as determined by pre-operative testing) that in the opinion of the investigator would confound the outcome(s) of the study
- 2) Any complication during cataract surgery (capsular tear, vitrectomy, etc)
- 3) History of or current retinal conditions or predisposition to retinal conditions
- 4) Amblyopia or strabismus in either eye
- 5) History of or current anterior or posterior segment inflammation of any etiology
- 6) Any form of neovascularization on or within the eye
- 7) Glaucoma (uncontrolled or controlled with medication)
- 8) Optic nerve atrophy
- 9) Subjects with diagnosed degenerative eye disorders
- 10) Postoperative CDVA worse than 0.10 logMAR in either eye.
- 11) Subjects who have an acute or chronic disease or illness that would confound the results of this investigation in the opinion of the principal investigator (e.g. immunocompromised, connective tissue disease, clinically significant atopic disease, etc)

EVALUATION CRITERIA:

The main objective of this study is to demonstrate that the Vivity IOL is well-tolerated with high patient satisfaction in patients who have had prior myopic refractive surgery with high spherical aberration.

Primary Clinical Endpoint:

Binocular Best Corrected Distance Visual Acuity

Secondary:

- 1) Monocular UCDVA, UCIVA (66 cm), UCNVA (40 cm)
- 2) Monocular BCDVA
- 3) Binocular Distance Corrected Intermediate (66cm) and near (40cm) Visual Acuity
- 4) Binocular UCDVA, UCIVA (66 cm), UCNVA (40 cm)
- 5) Unsolicited self-reported visual disturbances
- 6) QUVID questionnaire
- 7) Patient reported satisfaction by IOLSAT
- 8) Post-op refraction

Exploratory

- 1) Binocular BCDVA under mesopic room lighting conditions
- 2) Any SA changes pre cataract surgery and post cataract surgery
- 3) Binocular defocus curve
- 4) Spectacle independence (IOLSAT)

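### Exclusion 10 screens on achieved postoperative acuity, so it caps monocular BCDVA and indirectly bounds the primary endpoint, with no count of patients turned away

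*Protocol*

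**What the plan says.** - **Timing of entry.** Under Administration, patients who "have had bilateral Vivity IOLs implanted at the time of cataract surgery will be offered the opportunity to participate in the study". Inclusion 1 likewise requires that both eyes have already been operated on. Under Visit Schedule, "All subjects will undergo 1 visit".
- **The rule.** Exclusion 10 bars a patient with "Postoperative CDVA worse than 0.10 logMAR in either eye".
- **The endpoints.** The Primary Clinical Endpoint is "Binocular Best Corrected Distance Visual Acuity". Secondary endpoint 2 is "Monocular BCDVA".
- **The question.** The Background reports surgeons' worry that aberrations "may lead to decreased visual outcomes or increased visual disturbances". The Study Objectives set out to test that the lens "performs well in patients that had prior myopic refractive surgery and high residual SA after the refractive procedure".
- **A related criterion.** Inclusion 4 asks for "Best Corrected Distance Visual Acuity (BCDVA) projected to be 0.10 logMAR (Minimum Angle of Resolution) or better", without saying which data the projection uses.
- **Partial disclosure.** The Overall Study Design describes a cohort whose cataract surgery was successful and uncomplicated. It does not define successful.

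The protocol does not say whether exclusion 10 uses a chart value or the study-visit value. It does not ask for a count of patients who fail it.

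**The concern.** This is selection on an outcome, not on a baseline characteristic. A patient whose best corrected acuity fell short of 0.10 logMAR after implantation is an instance of the first half of the Background worry, and exclusion 10 removes that patient before any study data are collected. The poor end of the distribution is then missing from the endpoint meant to show whether it exists.

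The distortion is negligible if the hypothesis is true and grows as it fails. The enrolled data alone do not show which situation applies; the number turned away would. An analysis plan cannot recover patients who were never enrolled, so this has to be settled in the protocol.

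**Working it through.** **Logic.** Enrolment requires both eyes at 0.10 logMAR or better.

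- *Monocular BCDVA:* if eligibility is judged at the study visit, every enrolled eye is at 0.10 or better by construction. If an earlier chart value is used, the cap is approximate. The Administration text points towards chart values, because it offers entry to patients who already meet the inclusion criteria. All study testing, however, takes place at the single visit.
- *Binocular BCDVA:* the bound is indirect. It needs binocular acuity to be at least about as good as the better eye. Exclusion 4 (amblyopia, strabismus) makes that plausible, but the protocol does not state it.

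**Inputs.** From the protocol: the 0.10 logMAR limit in each eye, and n = 40 patients. The protocol gives no mean, SD or between-eye correlation. All of the following are assumptions:

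- Monocular BCDVA is bivariate normal, with between-eye correlation 0.5 or 0.8.
- The better eye (minimum logMAR) stands in for binocular acuity.
- Inclusion 4 acts first, on a projected value with the same mean, SD and between-eye correlation, correlated 0.3, 0.5 or 0.7 with the achieved value of the same eye.

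**Formulas.**

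- Share of eyes worse than the limit = 1 - Φ((0.10 - mean)/SD). For mean 0.00 and SD 0.08 this is 1 - Φ(1.25) = 11%.
- Shift = mean better-eye BCDVA after exclusion 10 minus the mean before it.
- CI half-width = t(0.975, 39) × SD of enrolled better-eye BCDVA / √40. For the second scenario this is 2.023 × 0.064 / 6.325 = 0.020.
- Failures per 40 enrolled = 40/(1 - share excluded) - 40. For 15.1% excluded this is 40/0.849 - 40 = 7.1.

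**Results with the inclusion 4 filter** (1,000,000 simulated patients per setting):

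| Assumed mean, SD | Eyes worse than 0.10, before any filter | Patients removed by exclusion 10 | Better-eye shift | CI half-width, n = 40 | Failures per 40 enrolled |
|---|---|---|---|---|---|
| -0.05, 0.06 (excellent) | 0.6% | 0.8-1.1% | -0.001 | 0.017-0.018 | under 1 |
| 0.00, 0.08 | 11% | 9-15% | -0.010 to -0.017 | 0.020-0.021 | 4-7 |
| 0.03, 0.10 (unfavourable) | 24% | 17-31% | -0.020 to -0.039 | 0.023 | 8-18 |
| 0.06, 0.12 (extreme) | 37% | 24-43% | -0.032 to -0.064 | 0.026 | 13-31 |

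**Limiting case.** If the projected value carried no information, so that inclusion 4 removed none of this tail, the shifts would be -0.001, -0.017 to -0.020, -0.043 to -0.047 and -0.073 to -0.080. The corresponding exclusions would be 1%, 15-18%, 32-37% and 47-53%. Mean monocular BCDVA would shift by -0.0015, -0.020, -0.049 and -0.083.

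**What the enrolled mean conceals.** In that limiting case at correlation 0.5, the better-eye means of the last three populations are -0.032, -0.010 and +0.012 before exclusion 10, and -0.049, -0.053 and -0.061 after it. Under these assumptions the worse population does not look worse once enrolled.

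**Chart-value variant.** With an assumed test-retest SD of 0.04 and no inclusion 4 filter, 91% to 99.5% of enrolled eyes still measure 0.10 or better at the study visit, and the better-eye shift is -0.001 to -0.077. The cap softens but does not disappear.

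**The case against.** Several objections carry weight.

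- **The cohort is declared as selected.** The Overall Study Design limits it to successful, uncomplicated surgery, and the protocol requires healthy eyes. Exclusion 10 could be read as making successful operational. This makes the restriction partly disclosed. It does not settle the matter, because the term is undefined and the objective and hypothesis are worded more broadly.
- **Exclusion 10 may be a backstop.** It can catch pathology that the other criteria miss; exclusion 1, for instance, relies on pre-operative testing. In a single-group study that has value, and it stands as a reason not to require removal.
- **The other criteria already trim the poor tail.** Clear media, retinal disease, glaucoma, optic atrophy and degenerative disorders are all screened, and the simulation does not model them. The larger figures rest on distributions that would be unfavourable or extreme for healthy eyes.
- **Much of the study is not directly capped.** Satisfaction and tolerability (the stated main objective), visual disturbances, mesopic, intermediate and near acuity and the defocus curve are outside the rule. Variation better than 0.10 logMAR stays visible.

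A reader might infer that exclusion 10 makes success on the primary endpoint certain. The protocol does not support that: it states no acuity threshold, margin or comparator for BCDVA, so meeting the entry rule satisfies no stated success criterion. Nor is it certain that no eye worse than 0.10 can appear in the data, since eligibility may rest on a chart value.

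**Conclusion.** The point holds for best corrected distance acuity. Exclusion 10 conditions entry on the achieved value of secondary endpoint 2: exactly if the study-visit value decides, approximately if a chart value does. It bounds the primary endpoint indirectly, on the better-eye assumption. Good BCDVA in the enrolled patients therefore cannot by itself show that the lens performs well in this population.

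Confidence is high in the mechanism and low in the size, which the protocol does not allow anyone to fix. With inclusion 4 taken into account, the shift is below sampling error in the two more favourable scenarios, straddles it in the unfavourable one, and is clearly above it only at the unfavourable to extreme end. A reader might take the limiting-case maximum (53% excluded, -0.080 logMAR) as the expected effect. That is not supported, because it combines an extreme assumed distribution with no contribution from inclusion 4.

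This should be fixed, because the remedy is cheap and the missing count is what would show whether the selection matters.

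**What to change.** 1. State in exclusion 10 which CDVA measurement decides eligibility: a chart value, with its timing, or the study-visit value.
2. Screen consecutive bilaterally implanted post-myopic LASIK/PRK patients and report how many fail exclusion 10 only. Add their chart BCDVA where consent or a waiver allows; a bare count is the fallback.
3. Limit the acuity conclusion to patients who already achieved 0.10 logMAR or better in each eye.

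The cost is protocol wording, light chart screening and a narrower acuity statement. No new procedures and no larger sample are needed.

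Dropping exclusion 10 is not required. The sponsor could choose to do so, basing inclusion 4 on preoperative data only and reporting BCDVA with and without eyes worse than 0.10 logMAR. The trade-off is that eyes with unrelated poor acuity may enter. Mean binocular BCDVA could also look worse, by about 0.001 to 0.064 logMAR under the assumptions above with inclusion 4 retained.
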